## **3.6 Investigational Product Discontinuation**

**Investigational product will be discontinued for a participant who meets any of the criteria below:**

- **Investigator believes that continuing treatment with investigational product is no longer in the participant's best interests (eg. due to significant AE related to investigational product).**
- **Participant withdraws assent.**
- **Participant's legal guardian withdraws consent.**
- **Pregnancy.**
- **Participant is unable to comply with the protocol, including completing required treatments, procedures, tests and/or examinations.**

**If a participant discontinues therapy with the investigational product they should be encouraged to continue with the study visit schedule if possible as they will be included in the Intention to Treat (ITT) analysis.**

## **3.7 Study and Site Discontinuation**

### **3.7.1 Study Discontinuation**

**Participants may be withdrawn from the study at any time at the Investigator's discretion, upon request from the Medical Monitor or at the participant's request. A participant or their legal guardian may withdraw consent at any time**

---

#### **Confidentiality Statement**

This document is confidential and is to be distributed for reference only to study staff, human research ethics committees and the applicable regulatory authorities. Information is not to be reproduced, abstracted or used for sharing of information for any purpose without with the written permission of the [name] or his delegate.

---

**without giving reasons. Withdrawal of consent to continue study participation shall not lead to any form of discrimination against the participant, in particular regarding medical care. If a participant withdraws their assent to participate in the study this will be respected by the Investigator, even if the participant's legal guardian maintains their consent for participation.**

**If a participant does not wish to continue with the study visits, study staff should attempt to schedule an Early Termination visit unless the participant discontinues at visit 1.**

**The reason for discontinuation should be recorded in the participant's source documents. If withdrawal is due to an AE the participant should be monitored for safety until the AE resolves or stabilises.**

### **3.7.2 Site Discontinuation**

The Investigator or the Therapeutic Goods Administration may stop the study for any reason. In the event that the study is terminated prematurely, written notification will be sent to the Human Research Ethics Committee (HREC) as soon as possible. The Investigator will promptly inform all participants and make arrangements for appropriate medical follow-up. All study materials will be returned to the study site by participants.

### **3.7.3 Replacement of Participants**

**Participants who prematurely discontinue from the study for any reason will not be replaced.**

## **3.8 Investigational Product Accountability and Disposition of Clinical Study Supplies**

**During the 2-week inpatient phase, an accountability log will be attached to each individual trial patient's medication chart with full explanation and documentation to nursing staff on administration and recording of trial drug. Should the patient be discharged on "Home IV", he/she will be given the remainder of the 2-week inpatient trial drug with full explanation of how it should be administered. At the 2-week review visit, the patient will be required to return all used and unused trial drug items, when pharmacy will perform a standard accountability log, before dispensing the 4-week outpatient batch of trial drug. At the 6-week review visit (4 weeks after cessation of IV antibiotic treatment)) the patient will again be requested to return all used and unused items for standard pharmacy accountability logging. A spare 3-day reserve supply will be issued to each patient to be kept separate from the main batch for use if the main batch is mislaid or damaged. Pharmacy will arrange appropriate**

---

**disposal of all collected used and unused trial drug items as per standard procedure.**

### **3.9 Study Blind and Un-blinding**

**This is a double-blind study, therefore neither the participants, study staff nor medical monitor will know which treatment has been assigned. The randomisation schedule will be generated by the statistician and kept securely by the pharmacist. The pharmacist will keep sealed envelopes with the treatment assignment for each participant to expedite un-blinding of individual participants if required.**

**In the case of a medical emergency where knowledge of the treatment assignment is essential to the welfare of the participant, the Principal Investigator (or appropriately- qualified designee) may request un-blinding of that participant by the pharmacist. A Treatment Un-blinding form will be completed by the Investigator to document the reason(s) for which it was necessary to break the blind.**

**The DSMC will have access to un-blinded data if required. Further information is provided in the DSMC Charter filed in the ISF.**

## **4. SUBJECT SELECTION**

**Once a decision is made by the treating physician to admit a cystic fibrosis patient to hospital and commence a standard course of intravenous and nebulised antibiotic treatment for a pulmonary exacerbation, the patient will be approached (with the treating physician's approval) to participate in the trial provided they meet the criteria outlined below.**

### **4.1 Inclusion Criteria**

- Male or female 6 years of age or older with a documented diagnosis of CF (positive sweat chloride test, genotype with two identifiable CF mutations) accompanied by one or more clinical features consistent with the CF phenotype.
- Current pulmonary exacerbation requiring antibiotic therapy.
- If older than 6 years, must be able to perform acceptable spirometric manoeuvres.
- FEV1 > 25% of predicted values (if older than 6 years of age).
- Positive sputum or bronchoalveolar lavage culture for *Ps aeruginosa* in the past 12 months.
- Must be able to give informed consent or have legally acceptable representative who can give informed consent in accordance with ICH/GCP.
- Females of child-bearing potential must agree to use an acceptable method of contraception for the duration of the trial.

---

## 4.2 Exclusion Criteria

- Known hypersensitivity to the investigational product or its components or known relevant medication allergy.
- Participation in another study with an investigational drug within 2 months of the planned first dose of investigational product.
- Known relevant substance abuse.
- Female patients who are pregnant or lactating
- Clinically significant disease or other medical condition other than CF or CF related conditions that would, in the opinion of the Investigator, compromise the safety of the patient or quality of the data.

Please note: The presence of additional bacterial or fungal organisms on sputum culture and/or the prescription of additional antibiotics (oral, intravenous, anti-pseudomonal, or non-anti-pseudomonal) at any stage through the trial will NOT affect inclusion into the trial)

## 4.3 Screening Failures and Rescreening

**Patients who fail screening may be approached again at the next admission to hospital for treatment of an exacerbation provided the factor(s) responsible for the first screen failure are thought to be not present any more.**

## 5. TREATMENT OF SUBJECTS

### 5.1 Study Drug Administration

**Patients will be randomly assigned to study drug or placebo. Study drug will consist of 2 ampoules – one containing Tobramycin 500 mg in 5 ml from which 2.5 ml will be withdrawn for each dose and second will be an ampoule containing 1.5 ml of a solution of Ca-EDTA and TRIS buffered saline from which 1.5 ml will be added to the 2.5 ml of Tobramycin immediately prior to use. The combined 4 ml will be nebulised until completed (~15 minutes). The comparator will also have 2 ampoules – Tobramycin (the same as in the treatment arm) and 1.5 ml of TRIS-buffered saline without Ca-EDTA.**

### 5.2 Study Drug Compliance

**Compliance will be monitored at each visit with the use of charts, simple questioning, diary cards and medication counts.**

### 5.3 Concomitant Therapies

In addition to the inhaled study drug, patients will continue with their standard CF care and medications (including any additional antibiotics at the discretion of the treating physician, as well as other forms of inhaled therapy such as Pulmozyme and hypertonic saline if necessary). All concomitant medications will be recorded throughout the study.

---

## 6. STUDY EVALUATIONS

The initial screening visit will assess patient eligibility for the study and ensure that the patient is fully aware of the aims, risks and possible benefits of the study before obtaining signed consent. At each subsequent visit, evaluations will be focused on collecting data and assessing the patient for (a) safety and (b) efficacy.

Screening visit:

**(a) Safety:**

- Ensure patient is willing, fit and able to participate in and likely to complete the study
- Meets eligibility criteria
- Has signed consent
- Has no conditions likely to be complicated by participating in the study
- Treating physician agrees to patient participating in trial
- History, physical assessment, vital signs, spirometry
- Baseline safety blood tests performed

**(b) Efficacy:**

- nil

Visit 1: (within 48 hours of Screening visit)

**(a) Safety:**

- Patient observed and respiratory signs and symptoms checked pre-, and half, 1 and 2 hours post-, first dose
- Spirometry pre-, and half, 1 and 2 hours post-, first dose
- First dose of medication given
- Blood test – Tobramycin serum levels (at appropriate time post-IV and neb dose)
- Systems and vital signs check pre-, and half, 1 and 2 hours post-, first dose
- Symptom diary provided to patient/parent
- Concomitant medications noted

**(b) Efficacy:**

- Baseline sputum, clinical assessment and Spirometry performed prior to first dose
- Study medication written up and dispensed for duration of two week hospital stay – to be administered by nursing staff and monitored by pharmacy as per protocol provided.

Visit 2: (1 week after starting treatment)

**(a) Safety:**

---

### Confidentiality Statement

This document is confidential and is to be distributed for reference only to study staff, human research ethics committees and the applicable regulatory authorities. Information is not to be reproduced, abstracted or used for sharing of information for any purpose without with the written permission of the [name] or his delegate.

- 
- **Respiratory signs and symptoms checked pre- and half hour post-dose**
  - **Spirometry pre- and half hour post-dose**
  - **Tolerability, adverse events and diary card check**
  - **History, system examination and vital signs checked**
  - **Concomitant medications noted**

**(b) Efficacy**

- **nil**

**Visit 3: (at discharge from hospital and end of IV antibiotic treatment)**

**(a) Safety:**

- **Respiratory signs and symptoms checked pre- and half hour post-dose**
- **Spirometry pre- and half hour post-dose**
- **Tolerability, adverse events and diary card check**
- **History, system examination and vital signs checked**
- **Safety blood tests performed**
- **Concomitant medications noted**
- **CF Questionnaire applied**
- **Medication for 4-week home treatment period dispensed with appropriate instructions regarding storage and use as per protocol provided and explained to parent/patient.**
- **Emergency plan and phone numbers provided in case of emergency**

**(b) Efficacy:**

- **Respiratory symptoms and signs noted**
- **Spirometry recorded**
- **Sputum sample collected**
- **CF Questionnaire applied**

**Visit 4: (telephone call)**

**(a) Safety:**

- **Respiratory symptoms check**
- **Tolerability and adverse events check**
- **Concomitant medications noted**

**(b) Efficacy:**

- **Nil**

**Visit 5: (end of treatment visit – 4 weeks after discharge/6 weeks after starting treatment)**

**(a) Safety:**

- **Respiratory signs and symptoms checked**
- **Spirometry**
- **Tolerability, adverse events and diary card check**

---

**Confidentiality Statement**

This document is confidential and is to be distributed for reference only to study staff, human research ethics committees and the applicable regulatory authorities. Information is not to be reproduced, abstracted or used for sharing of information for any purpose without with the written permission of the [name] or his delegate.

- 
- **History, system examination and vital signs checked**
  - **Safety blood tests performed**
  - **Concomitant medications noted**
  - **CF Questionnaire applied**

**(b) Efficacy:**

- **Respiratory symptoms and signs noted**
- **Spirometry recorded**
- **Sputum sample collected**
- **CF Questionnaire applied**

**Visit 6 (follow-up safety and efficacy visit – 4 weeks after stopping trial medication)**

**(a) Safety:**

- **Respiratory signs and symptoms checked**
- **Spirometry**
- **Tolerability, adverse events and diary card check**
- **History, system examination and vital signs checked**
- **Safety blood tests performed**
- **Concomitant medications noted**
- **CF Questionnaire applied**

**(b) Efficacy:**

- **Respiratory symptoms and signs noted**
- **Spirometry recorded**
- **Sputum sample collected**
- **CF Questionnaire applied**

## **7. ASSESSMENT OF ENDPOINTS**

### **7.1 Assessment of Efficacy**

**Essentially, we will be comparing the efficacy of the trial medication relative to the comparator with regards to biofilm formation and *PsA* growth in sputum. For this purpose, sputum will be collected using the Induced Sputum Method (see protocol – Addendum A) at Screening, Visit3, Visit 5 and Follow-up. In patients where sputum is not able to be obtained by this method, a nasopharyngeal swab will be performed although it is recognised that this may limit the number and interpretation of some of the tests performed on this specimen. Some patients may for clinical reasons require bronchoalveolar lavage in which case these samples will be used. The collection, handling and storage of the sputum specimens is outlined in the Standard Operating Procedure (SOP) document included as Addendum B at the end of this protocol. Essentially each**

---

#### **Confidentiality Statement**

This document is confidential and is to be distributed for reference only to study staff, human research ethics committees and the applicable regulatory authorities. Information is not to be reproduced, abstracted or used for sharing of information for any purpose without with the written permission of the [name] or his delegate.

---

specimen will be homogenised with an equal volume of sputolysin, separated into measured aliquots for each of the specific tests or collection of tests, and stored in appropriate preservative media at -80 degrees centigrade for batch testing once all specimens have been collected. For most of the tests (particular the molecular testing) only very small quantities (50-100 microlitres) are needed.

- **Bacterial load will be assessed by:**
  - **Quantitative PCR (qPCR) using established RT-qPCR assays based on the housekeeping genes *oprL* and *clpX*. These will be performed at the Menzies Institute in Darwin through the Infectious Diseases laboratory at the Telethon Institute of Child Health research, and at [name] laboratory in Queensland.**
  - **CFU counts (bacterial colony forming unit counts) performed in our microbiology laboratory at Princess Margaret Hospital.**

**Routine cultures for clinical assessment (if and as required by the treating physician) will be performed separately and will not be affected by this study.**

- **Biofilm production will be assessed by:**
  - **Imaging techniques using confocal light microscopy using a recently validated procedure at TICHR**
  - **[name]'s laboratory:**
    - **pyoverdinin and pyochelin assays will be used as a measure of iron utilisation in biofilm production.**
    - ***PsA* expression of iron-related virulence genes and RT-qPCR assays based on the housekeeping genes *oprL* and *clpX*.**
    - **In addition, as added insurance to exclude generation of a more aggressive *PsA* as a result of iron starvation, they will be quantifying the transcripts for the following virulence genes: *algD* (alginate synthesis), *hcnB* (cyanogenesis), *lasI* and *rhII* (quorum sensing regulators of biofilm production) and *lasB* (proteolytic enzyme)**
  - **Morphological characteristics of biofilm on culture**
- **Changes in MIC to a range of antibiotics (including particularly Tobramycin) will be done in our laboratory at PMH using standardised commercially available kits.**
- **Clinical comparisons using:**
  - **a standardised CF questionnaire**
  - **assessment of respiratory signs and symptoms at each visit**
  - **changes in FEV1 on spirometry measurements**

---

**Additional exploratory endpoints (subject to results of above endpoints and availability of future funding) may include:**

- **Assessment of inflammatory markers performed in our lab at TICHR**
- **Measurement of expression of genetic markers of beta-lactamase production by *PsA* – again using genetic markers validated at [name] laboratory in Brisbane.**

## **7.2 Assessment of Safety**

- Systemic
  - blood tests: FBC, LFT’s, U&E’s, Ca, Mg
  - history and general physical examination (including vital signs) at visits
- Local respiratory:
  - Symptoms – CF questionnaire
  - Symptoms (cough, wheeze and chest tightness) and physical examination (respiratory) at visits pre- and half-hour post-dose
  - Spirometry: change in FEV1 between pre- and half, 1, and 2 hours post-dosing with the first dose, and then pre- and half hour post-dosing at subsequent visits.
- Microbiome:
  - Monitoring of possible changes in *PsA* virulence factors, iron utilization and microbiome as a result of treatment (See paragraph above “Biofilm production assessed ....” In [name] laboratory in Brisbane

## **Notes on Pulmonary Function Testing as part of the safety assessment**

- The study will include patients 6 years and older although only patients 7 years and older will be required to perform spirometry.
- While in hospital spirometry will be performed at the patient’s bedside using a portable spirometer by a qualified technician using Knudsen reference values and according to ATS/ERS guidelines. During clinic visits spirometry will be performed using the same spirometer in the Respiratory Laboratory at Princess Margaret Hospital.
- A drop in post-dose FEV1 of >15% after the first dose or any subsequent dose will result in the patient been given appropriate treatment with Ventolin and if the event is deemed to be possibly or definitely related to the drug, he/she will be withdrawn from the study.
- Similarly, if any patient who is unable to perform spirometry exhibits any adverse respiratory or systemic signs or symptoms after the first or any subsequent dose, the event will be treated appropriately, and, if the event is deemed to be possibly or definitely related to the drug, he/she will be withdrawn from the study.

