**Confidentiality Statement**

This document is confidential and is to be distributed for reference only to study staff, human research ethics committees and the applicable regulatory authorities. Information is not to be reproduced, abstracted or used for sharing of information for any purpose without with the written permission of the [name] or his delegate.

---

possibly never unless he increased the concentration. Therefore this study cannot be used to negate or dictate the concentration chosen for our study. Additionally, even the placebo in this study showed more bronchoconstrictor activity than EDTA – remembering that the patients used were highly sensitive asthmatics.

8. The Beasley study involved six patients who had shown paradoxical bronchoconstriction to an inhaled bronchodilator containing small amounts of the preservative benzalkonium chloride (a known bronchoconstrictor) and EDTA. Paradoxical bronchoconstriction is extremely rare and occurs only in a small subgroup of highly sensitive asthmatics – almost always as a result of the benzalkonium chloride and not the EDTA. It is unique to asthma and has never been described in CF. We consider that, outside of this rare group of patients, the chances of finding this degree of airway hypersensitivity in any patient, including CF patients) are negligible. However, Beasley does also show that this bronchoconstriction can be successfully attenuated by prior administration of (preservative-free) albuterol (salbutamol), and on this basis, we have modified our protocol to include this option if necessary (see Section 7.2 Assessment of Safety). The Beasley study also used plain EDTA (not Ca-EDTA), unbuffered and with unknown tonicity – all of which could have added to the bronchoconstrictor activity, and all of which are corrected in our study drug. Another comment in the paper estimates that EDTA (in this form) is ~50 times weaker than histamine as a bronchoconstrictor, although again this is based on this uniquely sensitive group of patients.
9. However, Beasley also performed another study looking at 18 “normal” asthmatics (not with paradoxical bronchoconstriction) using inhaled formoterol and ipatropium bromide (Duovent) with and without 0.5mg/ml of EDTA. No significant difference in airway response was seen among the solutions.

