### **9.1.4 Relationship to Investigational Product**

The relationship, or attribution, of an AE to the investigational product will be determined by the Investigator. The relationship of the AE to the investigational product will be coded according to the following definitions:

**Unrelated:** The adverse event is due to an underlying or concurrent illness or effect of another drug and is clearly not related to the investigational product (eg. has no temporal relationship to study drug or has a much more likely alternative aetiology).

**Unlikely:** The adverse event has little or no temporal relationship to the study drug and a more likely aetiology exists.

**Possibly:** The adverse event has a strong temporal relationship to study drug and an alternative aetiology is equally or less likely compared to the potential relationship to study drug.

**Probably:** The adverse event has a strong temporal relationship to study drug or recurs on re-challenge. Aetiology is unlikely or significantly less likely.

The Investigator should attempt to provide an alternative aetiology for all AE's considered to be unrelated, unlikely or possibly related to study drug. This will be recorded in the source documentation.

For the purposes of reporting to the relevant regulatory agencies, unrelated and unlikely AE's will be classified as Not Related, while Possibly and Probably related will be reported as Related.

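### Section 7.2 withdraws a patient with a drug-related acute reaction from the study, whereas section 3.6 stops only the product and keeps the visits, so later sputum and safety data could be lost for a treatment-related reason

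*Protocol*

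**What the plan says.** **Section 7.2, Notes on Pulmonary Function Testing.** The first trigger is "A drop in post-dose FEV1 of >15% after the first dose or any subsequent dose". The second, for patients unable to perform spirometry, is any adverse respiratory or systemic sign or symptom after any dose. In both cases the event is treated and, "if the event is deemed to be possibly or definitely related to the drug, he/she will be withdrawn from the study".

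**Section 3.6, Investigational Product Discontinuation.** A significant adverse event related to the product is given as an example of a reason to discontinue the product. For participants who stop, "they should be encouraged to continue with the study visit schedule if possible as they will be included in the Intention to Treat" analysis.

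**Section 3.7.1, Study Discontinuation.** For participants who do not want further visits, "study staff should attempt to schedule an Early Termination visit unless the participant discontinues at visit 1". It adds: "If withdrawal is due to an AE the participant should be monitored for safety until the AE resolves or stabilises".

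**Section 3.7.3.** "Participants who prematurely discontinue from the study for any reason will not be replaced".

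**Section 10.1.2.** The efficacy population is the mITT set, meaning everyone randomised who took at least one dose.

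**The concern.** The same kind of event leads to two different dispositions. The protocol itself separates stopping the product (3.6) from leaving the study (3.7.1), so the wording in 7.2 cannot be passed over as a loose synonym. Staff dealing with a reaction are likely to follow the specific, mandatory rule in 7.2.

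The patients affected have been dosed, so they count in the mITT set, yet their later outcomes would not be collected. Both arms inhale tobramycin, so reactions can occur in either arm. If Ca-EDTA affects the airways, however, the losses could be unequal and related to treatment. Sputum also serves safety here, because the Synopsis and section 7.2 list *PsA* virulence factors and microbiome changes among the safety measures. An analysis plan can choose how to handle missing values, but it cannot recover samples that were never taken.

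**Working it through.** **1. The rules side by side**

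| | Section 7.2 | Section 3.6 |
|---|---|---|
| Event | Acute post-dose event, possibly or definitely drug-related | Significant product-related AE (given as an example) |
| Disposition | Withdrawn from the study | Product stopped |
| Later visits | End, if read literally | Encouraged, where possible |

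No section says which one governs.

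**2. Does section 3.7.1 close the gap?** It follows the triggering event until it resolves or stabilises, but that does not preserve later scheduled sputum, bloods or spirometry. Its Early Termination visit is written for participants who do not wish to continue. On a narrow reading it does not apply to a mandatory withdrawal at all. On a broad reading it applies but excludes anyone who discontinues at Visit 1. Visit 1 is the first dose, with spirometry at half, 1 and 2 hours (section 6). A first-dose reactor is uncovered on either reading.

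**3. Scheduled data lost if 7.2 is followed.** Post-baseline sputum is due on Days 15, 43 and 71 (Table of Study Assessments).

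- Reaction on Day 1: 71 − 1 = 70 days (10 weeks), 3 samples. Only baseline sputum exists, so no change in bacterial load can be computed.
- Reaction on Day 8: 71 − 8 = 63 days (9 weeks), 3 samples.
- Reaction on Day 15, with that day's sputum already taken: 71 − 15 = 56 days (8 weeks), 2 samples.

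**4. The plan's own power figure.** Inputs: 16 per group (Synopsis), alpha 0.05 and a difference of one SD (section 10.1.2). Two-sided testing is assumed. By the normal approximation:

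- n per arm = 2 × (1.960 + 0.842)² / 1² = 15.7, rounded up to 16, or 32 in total.
- Power at 16 per arm = Φ(√(16/2) − 1.960) = Φ(0.868) = 0.807.

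The stated 32 patients and 80% power are reproduced. A t-test at 16 per arm gives 0.781.

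**5. Power if patients are lost from one arm.** The number lost is an assumption.

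| Lost of 16 | Normal | t-test |
|---|---|---|
| 0 | 0.807 | 0.781 |
| 1 | 0.795 | 0.767 |
| 2 | 0.780 | 0.751 |
| 3 | 0.764 | 0.733 |

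Assumed drug-related reaction rates of 5%, 10% and 20% would give 0.8, 1.6 and 3.2 expected withdrawals among 16 patients. The chance of at least one, 1 − (1 − p)¹⁶, would be 56%, 81% and 97%.

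**6. Shift of the arm mean.** If k of 16 patients are lost and their mean would differ from that of the remaining patients by D, the observed arm mean differs from the full arm mean by (k/16) × D. Both k and D are assumed. The last column multiplies by 2.6, reading 2.6 log10 CFU/g as one SD.

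| k | D (SD) | Shift (SD) | Shift (log10 CFU/g) |
|---|---|---|---|
| 2 | 0.5 | 0.0625 | 0.16 |
| 2 | 1 | 0.125 | 0.33 |
| 3 | 0.5 | 0.094 | 0.24 |
| 3 | 1 | 0.1875 | 0.49 |

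**7. Two related wording checks**

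- Section 9.1.4 has no grade called definitely. Its related grades are Possibly and Probably, the latter defined by "The adverse event has a strong temporal relationship to study drug or recurs on re-challenge" together with an unlikely alternative cause. A literal reader of 7.2 has no instruction for Probably.
- Section 1.6.2(b), item 8, discusses bronchodilator given beforehand and says "we have modified our protocol to include this option if necessary (see Section 7.2 Assessment of Safety"). Section 7.2 provides only Ventolin after the event.

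**The case against.** The two sections can be read together: 3.6 as a soft general rule, and 7.2 as a stricter rule for one kind of event in children. The protocol does provide for AE-driven study withdrawal elsewhere. Section 3.7.1 allows it at the investigator's discretion and section 10.1.3 lists such events. A team might also prefer not to induce sputum in a child who has just had bronchoconstriction. But the protocol does not give that reason, and section 7.1 offers a nasopharyngeal swab as a fallback. Stopping the drug at once protects the child without ending follow-up.

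Three limits on the point stand:

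- **Narrow second trigger.** Patients older than 6 must be able to do spirometry (section 4.1), so this trigger concerns mainly six-year-olds.
- **The event itself stays covered.** Section 9.1.2 follows product-related events until resolved or clinically stable, and section 9.2.2 reports SAEs until the follow-up visit. The exposure is to later scheduled sputum, bloods, spirometry and visits.
- **The frequency is unknown.** The protocol reports that 50 mM EDTA was tolerated without adverse effects in 10 CF patients, so zero events is plausible, and the loss would then be nil. The log10 shift also depends on an ambiguous reading of 2.6 log10 in section 10.1.2.

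These points bear on how much data might be lost. They do not remove the conflict between the sections.

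**Conclusion.** The concern holds. Sections 7.2 and 3.6 give conflicting instructions for a drug-related acute reaction. Following 7.2 as written would end scheduled sputum and routine safety visits for dosed mITT patients for a reason tied to treatment. The contradiction is certain from the text.

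Its numerical effect is conditional. Each reactor loses 8 to 10 weeks of scheduled follow-up and 2 or 3 sputum samples in the cases worked above. The power loss is small, at most about 5 points by t-test if 3 of 16 are lost from one arm. The possible shift in that arm's mean, 0.06 to 0.19 SD, rests on an assumed 2 or 3 losses and an assumed 0.5 to 1 SD difference. The avoidable treatment-related missingness is the reason to fix it, more than the power. The grade and bronchodilator mismatches are genuine but only editorial.

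**What to change.** In both bullets of the section 7.2 notes, replace withdrawal from the study with stopping study drug. Add that the patient is encouraged to continue all scheduled visits, sputum and safety assessments to Day 71 unless consent or assent is withdrawn, in line with section 3.6. Use the section 9.1.4 grades: possibly or probably related.

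Secondary: either add the bronchodilator pre-treatment option to section 7.2 or correct the cross-reference in section 1.6.2(b), item 8.

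The cost is protocol wording only. The visits and samples are already in the schedule, and the reacting child still stops the drug at once.
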